Safety Outcomes

One secondary objective of the study is to assess the safety of interstitial injection of IC2000 for intraoperative lymphatic mapping. Tables 9, 10, and 11 summarize the data to address this secondary objective. These analyses will be performed on the safety (S) analysis set. Adverse events include Adverse Device Effects.

Table 9. Summary of Adverse Events				
Concise Term	Intensity	Relationship to Study Drug / Surgery	Number of Adverse Events	
			B-P Arm	P-B Arm
Term #1	Mild	Not Suspected		
	Moderate	Not Suspected		
	Severe	Not Suspected		
	Mild	Related to Blue Dye		
	Moderate	Related to Blue Dye		
	Severe	Related to Blue Dye		
	Mild	Related to Fluorescent Dye		
	Moderate	Related to Fluorescent Dye		
	Severe	Related to Fluorescent Dye		
	Mild	Related to Surgery		
	Moderate	Related to Surgery		
	Severe	Related to Surgery		
Term #2	Mild	Not Suspected		
	Moderate	Not Suspected		
	Severe	Not Suspected		
	Mild	Related to Blue Dye		
	Moderate	Related to Blue Dye		
	Severe	Related to Blue Dye		
	Mild	Related to Fluorescent Dye		
	Moderate	Related to Fluorescent Dye		
	Severe	Related to Fluorescent Dye		
	Mild	Related to Surgery		
	Moderate	Related to Surgery		
	Severe	Related to Surgery		
Etc.				
Total				

We will use Fisher’s exact test to compare study arms with respect to the distribution of intensity and relationship to study drug/surgery for each adverse event. We will estimate the incidence of each adverse event with a 95% exact binomial confidence interval.

Maximum Intensity	B-P Arm		P-B Arm		Total	
	N	%	N	%	N	%
Mild						
Moderate						
Severe						
Total						

We will use Fisher’s exact test to compare the distribution of maximum intensity of adverse events between study arms. We will estimate the percent of subjects with each maximum intensity level with a 95% exact binomial confidence interval.

We will provide a listing of all adverse events by study arm and subject, as shown in Table 11.

Arm	Subject	Concise Term	Intensity	Date of Onset	Date Resolved	Action Taken	Relationship to Study Drug / Surgery	Outcome

Protocol Deviations

We will list all protocol deviations for patients screened and enrolled on the study.

Arm	Subject	Date	Deviation	Other ...	Description	Severity

Other Data Summaries

We will provide listings of conditions, illnesses, or surgical procedures from the subjects' baseline medical history by subject and study arm (Table 13).

We will provide listings of concomitant medications by subject and study arm (Table 14).

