### 10.2 Hypotheses

To assess the effectiveness of PINPOINT in the identification of LNs, a non-inferiority test will be performed using the per-protocol (PP) analysis population.

$$\begin{aligned} H_{01}: \quad p_t &\leq p_c - 0.05 \\ H_{11}: \quad p_t &> p_c - 0.05 \end{aligned}$$

Here  $p_t$  and  $p_c$  represent the effectiveness of LN mapping with PINPOINT and Blue dye respectively. We define the numerator for  $p_t$  as the number of nodes identified with PINPOINT (classifications 1, 3, 5, 7 as defined in section 8.3.1.5) and confirmed as lymphoid tissue, and we define the numerator for  $p_c$  as the number of nodes identified with Blue dye (classifications 2, 3, 6, 7 as defined in section 8.3.1.5) and confirmed as lymphoid tissue. We define the denominator for both  $p_t$  and  $p_c$  as the number of nodes identified by ANY method (classifications 1-7 as defined in section 8.3.1.5). The denominator will include excised nodes confirmed as lymphoid tissue.

A non-inferiority margin of 0.05 was determined to be clinically significant based on feedback from Investigators. Within their respective groups,  $p_t$  and  $p_c$  represent the proportion of LNs identified (and confirmed to be lymphoid tissue, See [Section 8.5](#)) with PINPOINT and Blue dye respectively divided by the total number of LNs identified and excised, across all subjects.

We will repeat the analysis described above using the as-treated (AT) analysis set as a supporting analysis of the primary outcome.

As a sensitivity analysis we will also perform the non-inferiority test using the mITT analysis set. We will also perform sensitivity analyses of the primary endpoint using a best-case and a worst-case scenario. The best-case scenario will consider nodes with missing histology to be lymphoid tissue for PINPOINT and non-lymphoid tissue for Blue dye. The worst case scenario will consider nodes with missing histology to be non-lymphoid tissue for PINPOINT and lymphoid tissue for Blue dye.

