## 10.6 Secondary Objectives

The planned secondary outcomes are intended to support product labelling. We will use the step-down method described by Benjamini and Liu to control the false discovery rate at 0.05 (2-sided) while testing our secondary objectives.

The first secondary outcome is the ability of PINPOINT and Blue dye to detect at least one lymph node in a subject.

Let  $q_t$  and  $q_c$  represent the proportion of subjects with at least one lymph node identified (according to [section 8.3.1.5](#) and confirmed by histology) with PINPOINT and Blue dye respectively, divided by the total number of subjects where mapping was attempted. That is, the numerator for  $q_t$  is the number of subjects with at least 1 node identified with PINPOINT (classifications 1, 3, 5, 7) and confirmed as lymphoid tissue, and the numerator for  $q_c$  is the number of subjects with at least 1 node identified with Blue dye (classifications 2, 3, 6, 7) and confirmed as lymphoid tissue. The denominator of both  $q_t$  and  $q_c$  is the number of subjects where mapping was attempted.

The following hypotheses will be tested:

$$\begin{aligned} H_{03}: q_t &\leq q_c - 0.05 \\ H_{13}: q_t &> q_c - 0.05 \end{aligned}$$

To test this hypothesis we will estimate the difference  $q_t - q_c$  with a 95% two-sided confidence interval. We will perform this analysis using the PP analysis set to test the inferiority hypothesis ( $H_{03}$ ) stated above, and if the lower bound of the interval is greater than -0.05 we will claim non-inferiority. If and only if we reject the inferiority hypothesis ( $H_{03}$ ) we will use the mITT analysis set to test for superiority, and if the lower bound of the interval is greater than 0 we will claim superiority.

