Adenosquamous Carcinoma						
Neuroendocrine						
Clear Cell Carcinoma						
Undifferentiated						
Mixed						
Surgical Procedure						
Hysterectomy						
Radical Hysterectomy						
Radical Trachelectomy						
Bilateral Salpingo-Oophorectomy						
Unilateral Salpingo-Oophorectomy						
Ovarian Transposition						
Sentinel Node Mapping						
Pelvic Node Sampling						
Pelvic Node Dissection						
Para-Aortic Node Sampling						
Para-Aortic Node Dissection						
Other						
Length of Surgery (minutes)						
Median (Min – Max)						
Dose of IC2000 (mg)						
Median (Min – Max)						
Dose of Blue Dye (mg)						
Median (Min – Max)						

Primary Efficacy Outcome

The primary objective of this study is to assess the effectiveness of intraoperative PINPOINT Near Infrared Fluorescence Imaging (PINPOINT) in identification of LNs in subjects with uterine and cervical malignancies who are undergoing LN mapping. Table 3 summarizes the study primary outcome.

Table 3. Lymph Nodes Identified						
Identification Method	B-P Arm		P-B Arm		Total	
	N	%	N	%	N	%
PINPOINT Only						
Confirmed as NOT Lymphatic Tissue						
Confirmed as Lymphatic Tissue						
Confirmed as Lymphatic Tissue (negative for cancer)						
Confirmed as Lymphatic Tissue (positive for cancer)						
Blue Dye Only						
Confirmed as NOT Lymphatic Tissue						
Confirmed as Lymphatic Tissue						
Confirmed as Lymphatic Tissue (negative for cancer)						
Confirmed as Lymphatic Tissue (positive for cancer)						
Both PINPOINT and Blue Dye						
Confirmed as NOT Lymphatic Tissue						
Confirmed as Lymphatic Tissue						
Confirmed as Lymphatic Tissue (negative for cancer)						
Confirmed as Lymphatic Tissue (positive for cancer)						
Following a Fluorescent Duct (No Dye Present in Node)						
Confirmed as NOT Lymphatic Tissue						
Confirmed as Lymphatic Tissue						
Confirmed as Lymphatic Tissue (negative for cancer)						
Confirmed as Lymphatic Tissue (positive for cancer)						
Following a Fluorescent Duct (Blue Dye Present in Node)						
Confirmed as NOT Lymphatic Tissue						
Confirmed as Lymphatic Tissue						
Confirmed as Lymphatic Tissue (negative for cancer)						
Confirmed as Lymphatic Tissue (positive for cancer)						
Following a Blue Duct (No Dye Present in Node)						
Confirmed as NOT Lymphatic Tissue						
Confirmed as Lymphatic Tissue						
Confirmed as Lymphatic Tissue (negative for cancer)						
Confirmed as Lymphatic Tissue (positive for cancer)						

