Following a Blue Duct (Fluorescent Dye Present in Node)						
Confirmed as NOT Lymphatic Tissue						
Confirmed as Lymphatic Tissue						
Confirmed as Lymphatic Tissue (negative for cancer)						
Confirmed as Lymphatic Tissue (positive for cancer)						
Following a Blue and Fluorescent Duct (No Dye Present in Node)						
Confirmed as NOT Lymphatic Tissue						
Confirmed as Lymphatic Tissue						
Confirmed as Lymphatic Tissue (negative for cancer)						
Confirmed as Lymphatic Tissue (positive for cancer)						

Table 3. Lymph Nodes Identified

Identification Method	B-P Arm		P-B Arm		Total	
	N	%	N	%	N	%
Appearance (No Dye Present in Node)						
Confirmed as NOT Lymphatic Tissue						
Confirmed as Lymphatic Tissue						
Confirmed as Lymphatic Tissue (negative for cancer)						
Confirmed as Lymphatic Tissue (positive for cancer)						
Total						
PINPOINT						
Confirmed as NOT Lymphatic Tissue						
Confirmed as Lymphatic Tissue						
Blue Dye						
Confirmed as NOT Lymphatic Tissue						
Confirmed as Lymphatic Tissue						
Neither Dye						
Confirmed as NOT Lymphatic Tissue						
Confirmed as Lymphatic Tissue						
Total						

To assess the effectiveness of PINPOINT in the identification of LNs, a non-inferiority test will be performed using the per-protocol (PP) analysis set.

$$H_{01}: p_t \leq p_c - 0.05$$

$$H_{11}: p_t > p_c - 0.05$$

Here p_t and p_c represent the effectiveness of LN mapping with PINPOINT and Blue dye respectively. We define the numerator for p_t as the number of nodes identified with PINPOINT (i.e., with PINPOINT alone or with both Blue dye and PINPOINT) and confirmed as lymphoid tissue, and we define the numerator for p_c as the number of nodes identified with Blue dye (i.e., with Blue dye alone or with both Blue dye and PINPOINT) and confirmed as lymphoid tissue. We define the denominator for both p_t and p_c as the number of nodes identified by ANY method (i.e., PINPOINT alone, Blue dye alone, both Blue dye and PINPOINT, abnormal appearance or palpably hard, non-stained node found at termination of Fluorescent duct, non-stained node found at termination of Blue duct, non-stained node found at termination of duct stained with both Blue dye and Fluorescent dye). The denominator will include excised nodes confirmed as lymphoid tissue.

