The first secondary outcome is the ability of PINPOINT and Blue dye to detect at least one lymph node in a subject. Let q_t and q_c represent the proportion of subjects with a least one node identified and confirmed as lymphoid tissue with PINPOINT and Blue dye respectively, divided by the total number of subjects where mapping was attempted. That is, the numerator for q_t is the number of subjects with at least 1 node identified with PINPOINT (PINPOINT alone, both Blue dye and PINPOINT, non-stained node found at termination of Fluorescent duct, Blue-stained node found at termination of a Fluorescent duct, non-stained node found at termination of duct stained with both Blue dye and Fluorescent dye) and confirmed as lymphoid tissue, and the numerator for q_c is the number of subjects with at least 1 node identified with Blue dye (Blue dye alone, both Blue dye and PINPOINT, non-stained node found at termination of Blue duct, Fluorescent-stained node found at termination of Blue duct, non-stained node found at termination of duct stained with both Blue dye and Fluorescent dye) and confirmed as lymphoid tissue. The denominator of both q_t and q_c is the number of subjects where mapping was attempted.

Table 4 summarizes the data to address this secondary objective.

Table 4. Number of Subjects with ≥ 1 Lymph Node Identified						
Identification Method	B-P Arm		P-B Arm		Total	
	N	%	N	%	N	%
PINPOINT						
Blue Dye						
Number of Subjects						

We will test the following hypotheses:

$$H_{03}: q_t \leq q_c - 0.05$$

$$H_{13}: q_t > q_c - 0.05$$

To test this hypothesis we will estimate the difference $q_t - q_c$ with a 95% two-sided confidence interval. We will perform this analysis using the PP analysis set to test the inferiority hypothesis (H_{03}) stated above, and if the lower bound of the interval is > -0.05 we will claim non-inferiority. If and only if we reject the inferiority hypothesis (H_{03}) we will use the mITT analysis set to test for superiority, and if the lower bound of the interval is > 0 we will claim superiority.

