A third secondary outcome is the proportion of LNs identified by following lymphatic channels (ducts). Let d_t and d_c represent the proportion of nodes identified by following a duct and confirmed as lymphoid tissue with PINPOINT and Blue dye, respectively. That is, the numerator for d_t is the number of nodes identified with PINPOINT by following a duct (non-stained node found at termination of Fluorescent duct, Blue-stained node found at termination of a Fluorescent duct, non-stained node found at termination of duct stained with both Blue dye and Fluorescent dye) and confirmed as lymphoid tissue. Similarly, the numerator for d_c is the number of nodes identified with Blue dye by following a duct (non-stained node found at termination of Blue duct, Fluorescent-stained node found at termination of a Blue duct, non-stained node found at termination of duct stained with both Blue dye and Fluorescent dye) and confirmed as lymphoid tissue. We define the denominator for both d_t and d_c as the number of nodes identified by ANY method. The denominator will include excised nodes confirmed as lymphoid tissue.

Table 6 summarizes the data to address this secondary objective.

Table 6. Number of Subjects with Lymph Nodes Identified by Following a Duct

Identification Method	B-P Arm		P-B Arm		Total	
	N	%	N	%	N	%
PINPOINT						
Blue Dye						
Number of Subjects						

We will test the following hypotheses:

$$H_{05}: d_t \leq d_c - 0.05$$

$$H_{15}: d_t > d_c - 0.05$$

To test this hypothesis we will estimate the difference $d_t - d_c$ with a 95% two-sided confidence interval. We will estimate this confidence interval in a manner similar to that described for the primary outcome. We will perform this analysis using the PP analysis set to test the inferiority hypothesis (H_{05}) stated above, and if the lower bound of the interval is > -0.05 we will claim non-inferiority. If and only if we reject the inferiority hypothesis (H_{05}) we will use the mITT analysis set to test for superiority, and if the lower bound of the interval is > 0 we will claim superiority.

We will also estimate overall percent agreement, positive percent agreement, and negative percent agreement with exact (Clopper-Pearson) 95% confidence intervals. The data will be summarized as shown in Table 7.

Table 7. Agreement of PINPOINT with Blue Dye

		Blue Dye (Reference)		Total
		(+)	(-)	
PINPOINT (Test)	(+)	A	B	A + B
	(-)	C	D	C + D
Total		A + C	B + D	

We define the following quantities:

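### The primary endpoint has two written definitions: the SAP numerators leave out the unstained duct-found nodes that Protocol 10.2 counts, and two Table 3 rows have no assigned place

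*SAP*

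**What the plan says.** Protocol 10.2 builds the primary numerators from the seven node classes of 8.3.1.5: "classifications 1, 3, 5, 7 as defined in section 8.3.1.5" for PINPOINT and "classifications 2, 3, 6, 7 as defined in section 8.3.1.5" for Blue dye. Classes 5, 6 and 7 are nodes that carry no dye themselves but lie at the end of a fluorescent duct, a blue duct, or a duct showing both. Protocol 10.6 uses the same list for the per-subject detection rate q: "at least 1 node identified with PINPOINT (classifications 1, 3, 5, 7) and confirmed as lymphoid tissue".

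The SAP (Primary Efficacy Outcome) tests the same hypothesis on the same p_t and p_c, but defines the first numerator as the "number of nodes identified with PINPOINT (i.e., with PINPOINT alone or with both Blue dye and PINPOINT) and confirmed as lymphoid tissue". The Blue dye numerator has the parallel wording. The denominator that follows lists "non-stained node found at termination of Fluorescent duct, non-stained node found at termination of Blue duct" as items separate from the dye-alone and both-dye nodes.

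Under Secondary Efficacy Outcomes the SAP credits duct-found nodes. The PINPOINT list for q includes "non-stained node found at termination of Fluorescent duct, Blue-stained node found at termination of a Fluorescent duct", the bilateral rate b does the same, and the duct outcome d counts the "number of nodes identified with PINPOINT by following a duct (non-stained node found at termination of Fluorescent duct" and related items.

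SAP Table 3 has a row "Following a Fluorescent Duct (Blue Dye Present in Node") and its mirror image for a fluorescent node at a blue duct. Neither exists among the seven protocol classes.

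**The concern.** In class terms the protocol uses 1+3+5+7 against 2+3+6+7, and the SAP uses 1+3 against 2+3. The SAP wording cannot be read as shorthand that includes duct nodes, because its denominator lists them as separate items. A class 5 node is therefore identified with PINPOINT in the SAP's q, b and d, but is a PINPOINT miss in p.

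The two cross-stain rows of Table 3 are named in neither primary numerator and are missing from the SAP's denominator list, so their effect on N is also unstated. The closing PINPOINT, Blue dye and neither-dye totals of Table 3 have no stated mapping from the rows.

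Non-inferiority (lower bound above -0.05) and superiority (lower bound above 0) both rest on p_t - p_c. Nothing in the available text says which document governs. Two analysts could follow the plan in good faith and report different primary results. In an open-label study, choosing between the definitions once node counts are known would be a post hoc choice.

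**Working it through.** **Inputs.** From Protocol 10.4: 525 nodes, 3.5 nodes per subject, ICC at most 0.125, planning rates 84% and 80%, literature averages 91% and 80%. From Protocol 10.2 and 10.3: margin 0.05 and a two-sided 95% interval. The documents give no counts for classes 4 to 7 or for cross-stain nodes, so every such count below is an assumption.

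**Plan's own figure.** VIF = 1 + (2 x 3.5 - 1) x 0.125 = 1.75 and ESS = 525/1.75 = 300. SE = sqrt((0.84 x 0.16 + 0.80 x 0.20)/300) = 0.0313. Power = Phi(0.09/0.0313 - 1.96) = 0.819, which agrees with the stated 82%. The sample-size arithmetic is not in question.

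**Gap between the definitions.**
- Protocol: p_t - p_c = (n1 + n5 - n2 - n6)/N.
- SAP: p_t - p_c = (n1 - n2)/N.
- Protocol minus SAP: (n5 - n6)/N. Class 7 cancels from the difference, though it changes p_t and p_c themselves.
- At N = 525 one percentage point is 5.25 nodes, and the margin is 0.05 x 525 = 26.25 nodes.

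**Effect on the lower bound.** I approximate the planned clustered interval by d - 1.96 x sqrt((f10 + f01 - d^2) x VIF/N), where f10 and f01 are the PINPOINT-only and Blue-only shares. With one matched pair per node, m = 3.5 and VIF = 1 + 2.5 x 0.125 = 1.3125; the protocol's 1.75 is shown beside it. Applying the protocol's ICC to the paired difference is an assumption, as is using one node set for PP and mITT.

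Base case: 84% and 80% hold under the protocol rule, with 4% (21 nodes) in class 4. Then 441 + 420 - 504 = 357 nodes count for both methods, 84 for PINPOINT only and 63 for Blue dye only. At VIF 1.3125: 0.04 - 1.96 x sqrt((0.28 - 0.0016) x 1.3125/525) = -0.0117.

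| Rule and assumed counts | PINPOINT-only / Blue-only | d (points) | Bound, VIF 1.3125 | Bound, VIF 1.75 | Verdict |
|---|---|---|---|---|---|
| Protocol | 84 / 63 | +4.00 | -1.17 | -1.97 | non-inferior, not superior |
| SAP, n5=5, n6=2 | 79 / 61 | +3.43 | -1.62 | -2.40 | unchanged |
| SAP, n5=10, n6=5 | 74 / 58 | +3.05 | -1.86 | -2.62 | unchanged |
| SAP, n5=10, n6=26 | 74 / 37 | +7.05 | +2.59 | +1.91 | superiority gained |
| SAP, n5=26, n6=5 | 58 / 58 | 0.00 | -4.61 | -5.32 | non-inferiority lost at 1.75 only |

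**Tipping points on this base** (VIF 1.75 in brackets). With n6 = 0, non-inferiority is lost at 23 (18) class 5 nodes. With n5 = 0, superiority is gained at 6 (10) class 6 nodes. As the class 4 share runs from 0% to 8%, these become 18 to 28 (13 to 24) and 9 to 2 (14 to 5).

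**At the 91% and 80% averages**, with 2% class 4, duct nodes of 5% against 1% lower the bound from +6.22 to +2.78 (+5.48 to +2.13), and both claims stand. With n6 = 0, superiority is lost only at 36 (33) class 5 nodes and non-inferiority only at 66 (63).

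**Cross-stain rows alone**, assuming 10 blue nodes at a fluorescent duct, 3 the reverse, no class 5 or 6 nodes, and N held at 525:
- Credited by the dye in the node: 84 / 63, bound -1.17 (-1.97).
- Credited to neither method or to both: 81 / 53, d = +5.33, bound +0.41 (-0.35).
- Credited by duct only: 91 / 56, d = +6.67, bound +1.52 (+0.73).

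**The case against.** There is a fair case for the SAP's stained-only rule. The identification criteria in Protocol 8.3.1.3 and 8.3.1.4 rest on seeing dye or fluorescence in the node, or on an abnormal node; ducts are followed only to find nodes to excise. Protocol 3.1 describes Blue dye effectiveness in terms of seeing the dye. The Table 3 row labels and the neither-dye total suggest a mapping by the dye present in the node. The duct outcome d must count duct nodes by construction, so it says little about p. The verdict-changing scenarios assume net imbalances of 16 and 21 nodes, and the smaller ones in the table change nothing.

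Much of this stands as argument for one of the two rules. It does not remove the conflict. Protocol 10.2 states its class lists explicitly for this endpoint, so the tension also lies inside the protocol. The mapping by dye is an inference, and the SAP's secondary section credits cross-stain nodes by duct. That section does not say whether a blue node at a fluorescent duct also counts as a dye-alone node for Blue dye. Setting d aside, q and b still use a different meaning of identification from p. The uncertainty about counts limits the predicted effect, not the defect.

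**Conclusion.** The concern holds, and this should be settled before analysis. The confirmatory estimand has two conflicting written definitions, and that finding rests on the text alone.

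The size is known only as a formula, (n5 - n6)/N, plus whatever the handling of the cross-stain rows adds. Its sign, magnitude and likelihood cannot be judged from the documents. If n5 = n6 and no cross-stain nodes occur, the point estimates agree, although the interval can still move: with 20 of each, the base-case bound goes from -1.17 to -0.41 at VIF 1.3125. Near the planning rates, modest imbalances could change a claim. Near the literature averages it would take a large one. All bounds depend on the matched-pair approximation, the assumed inflation factors and the assumed class shares.

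**What to change.** Before analysis:

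1. State one numerator rule by class number, in the same words, in Protocol 10.2 and the SAP primary section. The 10.2 lists are the natural default, being explicit and consistent with q and b on unstained duct nodes. If a stained-only rule is intended, amend 10.2 and explain why p differs from q, b and d.
2. Add a table that assigns every SAP Table 3 row, including the two cross-stain rows, to PINPOINT, Blue dye, both or neither, and to the denominator. Use one rule for p, q and b, say whether the rows are mutually exclusive, and derive the closing totals from it.
3. Report the other numerator definition as a labelled sensitivity analysis.

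The cost is some wording and one table. Table 3 already tabulates each row separately, so no new data are needed.
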